# report least square group differences
tmt.means <- emmeans(var_sec, ~ intervention * time)
contrast(tmt.means)
pairs(tmt.means)
```

Safety endpoints that are raised at baseline and at another visit will be analysed using group mean comparisons between the intervention groups (δ) adjusted for baseline assessments and centre in analysis of covariance (ANCOVA) models. Least square group differences will be reported with 95% CIs and p-values testing the null hypothesis of no intervention effect ($H_0: \delta = 0$).

```

library(emmeans)

mod.sec <- lm(var ~ intervention + var_baseline + site,
               data = secEndpoints)

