1.2 Objectives and Endpoints

POWER@MS2 investigates the hypothesis that the web- and evidence-based relapse management programme results in more autonomous relapse treatment decision-making by PwMS.

Clinical endpoints are evaluated by the trial statistician, while endpoints related to health economic aspects of the trial are evaluated by the Health Economics team and therefore not specified in this SAP. Primary, secondary and safety endpoints are listed in Table 1.

Table 1 Objectives and related endpoints

	Objective	Endpoint
Primary	To determine whether the programme leads to a decrease in corticosteroid relapse treatment and less intravenous administered corticosteroids in case of steroid treatment.	Proportion of relapses not treated or treated with oral corticosteroids during the follow-up.
Secondary	To determine whether the programme results in more autonomous relapse treatment decisions.	Differences in decision autonomy measured by CPS.
	To determine whether the programme leads to fewer relapses.	Annualised relapse rate.
	To determine whether the programme leads to an increase in risk-knowledge.	Changes in Risk Knowledge.
	To determine whether the programme leads to more empowerment.	Changes in empowerment measured by PAM from baseline to end of study.

	To determine whether the programme leads to a more autonomous steroid treatment decision-making	Changes in PBMS relapses.
Safety	Assessment of safety of the intervention	Changes in HAQUAMS. Changes in HADS. Changes in EDSS. Changes in UNDS.

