3.1 Confidence intervals and p-values

All tests will be performed two-sided on a significance level of 5%. Confidence intervals (CI) will be reported with 95% confidence level.

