5.2 Analysis methods

In the analysis of primary and secondary endpoints, centres with less than 10 patients are pooled into one centre.

The primary endpoint is analysed using a generalised linear model with mixed effects and logit link function. Subject-specific effects are modelled as random effects, while intervention group and study centre are included as fixed effects. In case of nonconvergence due to a flat likelihood in the variance of the subject-specific effects near 0, the model will be simplified by removing the random subject-specific effects resulting in a generalized linear model (logistic regression). In this case correction of standard errors by using generalized estimating equations (GEE) will be explored. The intervention effect is reported as odds ratio (OR) with 95% CI and p-value testing the null hypothesis of no intervention effect ($H_0: OR = 1$).

```
library(MASS)

prim.mod <- glmer(oral_treated ~ intervention + site + (1|Patient.Id),
                  data = primEnd, family = binomial(link = "logit"))
summary(prim.mod)
emmeans(prim.mod ~ intervention, type = "response")
```

Longitudinal assessments of the quality of life and impairment are analysed employing Gaussian linear models for repeated measures with intervention group, time, intervention-by-time interaction and study centre as factors and, if the instrument was assessed at baseline, its baseline score as a covariate (mixed model for repeated measurements, MMRM).

The error terms are assumed to follow a multivariate normal distribution with unstructured covariance matrix. Least squares mean changes from baseline will be reported for both groups with 95% CI as well as the difference between the least-squares intervention group means with 95% CI and p-value testing the null hypothesis of no treatment effect ($H_0: \delta = 0$).

```
library(lme4)
library(car)
library(emmeans)

var_sec <- lmer(var ~ baseline_var + intervention + time + intervention * time +
                  site + (1|Patient.Id), data = secEndpoints)
summary(var_sec)
res <- Anova(var_sec, type = "III", test.statistic = "F")
res

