# report least square group differences
tmt.means <- emmeans(mod.sec, ~ intervention)
tmt.means
pairs(tmt.means)

```

For the Control Preference Scale, ordinal regression with logit link will be used with intervention and study centre as covariates. The model assumptions will be checked.

```

library(ordinal)
library(emmeans)

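### For repeated-measures endpoints (chiefly UNDS) the group difference is tied to no visit or average, and the reporting code gives same-visit p-values with a Tukey adjustment the SAP never asks for

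*SAP*

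**What the plan says.** SAP section 5.2 analyses longitudinal quality-of-life and impairment scores with a repeated-measures model that has "intervention group, time, intervention-by-time interaction and study centre as factors", plus the baseline score where there is one. It promises "the difference between the least-squares intervention group means with 95% CI and p-value testing the null hypothesis of no treatment effect", written as a single delta equal to zero.

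Under the comment about reporting group differences, the R code builds the marginal means with "tmt.means <- emmeans(var_sec, ~ intervention * time") and then calls "contrast(tmt.means") and `pairs(tmt.means)`. Neither call has further arguments. Just before that, the block prints `summary(var_sec)` and a Type III F table.

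Section 3.1 states: "All tests will be performed two-sided on a significance level of 5"%. The SAP specifies no multiplicity adjustment.

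Table 1 in section 1.2 fixes the time span for PAM (baseline to end of study), but for the safety endpoint UNDS it says only "Changes in UNDS". Section 2.7 gives a follow-up of 12 to 36 months.

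**The concern.** With a group-by-time interaction there is one group difference per visit, and also an average over visits. A hypothesis about a single delta has no definite meaning until one of these is named. With follow-up varying between 12 and 36 months, end of study would itself need a definition.

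The code might be expected to supply the missing choice, but it does not. It compares every group-by-visit cell with every other cell and with the grand mean, and applies default adjustments over that whole family. Most of those comparisons, such as one group at month 15 against the other at month 30, are of no interest, yet they inflate the p-values of the comparisons that are. For a safety endpoint the main risk is that a real worsening at a given visit is reported as non-significant.

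**Working it through.** **Inputs.**
- Two groups, and time as a factor (section 5.2).
- Two-sided 5% tests (section 3.1).
- 146 patients (section 2.3), used only for the illustration.
- Number of post-baseline visits v: an assumption. As extracted, Table 2 marks UNDS at t5 to t12 plus tx, which is 8 + 1 = 9 levels. The table is broken, so v = 2, 3, 6 and 9 are shown.

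The plan gives no figure of its own on this point to reproduce.

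**Step 1: what the reporting lines produce.** There are k = 2v cells. Default `pairs()` gives k(k − 1)/2 comparisons with Tukey-adjusted p-values, of which only v are same-visit group differences. Default `contrast()` gives k cell-versus-grand-mean effects with FDR-adjusted p-values. For v = 9, k = 18, so there are 18 × 17/2 = 153 pairs, 9 of them same-visit, and 18 effects. Running these calls in R on simulated data (146 patients, 9 visits, site omitted) confirmed 153 and 18 rows. The footnotes name the Tukey method for a family of 18 estimates and the FDR method for 18 tests. The average group difference over visits is in neither table.

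**Step 2: effect of the Tukey adjustment.** For a same-visit statistic t, the printed p is P(Q > √2·|t|), where Q is the studentized range for k means. The critical |t| is q(0.95; k)/√2 instead of 1.96. With infinite df, and |t| = 2.576 for a raw p of 0.01:

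| Visits | Pairs | Critical \|t\| | Raw p 0.01 prints as | Raw p needed for printed p < 0.05 |
|---|---|---|---|---|
| 2 | 6 | 2.569 | 0.049 | 0.0102 |
| 3 | 15 | 2.850 | 0.10 | 0.0044 |
| 6 | 66 | 3.268 | 0.29 | 0.0011 |
| 9 | 153 | 3.489 | 0.47 | 0.0005 |

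With 144 df the fourth column becomes 0.049, 0.10, 0.28 and 0.45. In the simulated fit, the fourth-visit difference of 0.452 had a raw p of 0.024 and was printed with p = 0.71.

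**Step 3: the other printed output.** Under R's default coding, the intervention coefficient and the Type III intervention test refer to the first visit only. In the same fit the Type III p was 0.1027, identical to the raw first-visit p. The average over visits was 0.593 (95% CI 0.29 to 0.895, p = 0.0002). These outputs therefore do not supply delta either, unless the first visit was meant.

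**Step 4: the alternative, unadjusted p-values with delta left open.** Take exchangeable normal visit statistics with correlation ρ (assumed) and no true effect, and let the candidates be each visit and the standardised average. The chance that at least one has |Z| > 1.96, from 400,000 draws:

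| Visits | ρ = 0.9 | ρ = 0.7 | ρ = 0.5 |
|---|---|---|---|
| 2 | 0.071 | 0.086 | 0.098 |
| 3 | 0.084 | 0.110 | 0.129 |
| 6 | 0.108 | 0.163 | 0.209 |
| 9 | 0.124 | 0.203 | 0.270 |

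**Step 5: the two effects exclude each other.** Applying the Tukey critical values of step 2 to the same draws, the chance of any significant same-visit difference is about 1.5% to 2% with 2 visits and 0.2% to 0.4% with 9. Following the code is conservative; the inflation in step 4 arises only if the code's p-values are set aside.

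**The case against.** The strongest reply is that the interaction and the intervention-by-time means imply that the difference at every visit is to be reported. Nothing would then be selected, and the average would not be a candidate. That reading is reasonable, and it weakens any suggestion that a visit will be picked after the data are seen. It does not say which difference the single null hypothesis concerns, and it does not remove the Tukey adjustment from the printed p-values.

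A second reply is that the estimates and standard errors are right, the footnotes name the adjustments, and section 5.6 allows SAS, where these defaults do not apply. All of that stands. It limits the harm from the code but leaves delta undefined in either package.

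A third reply is that a false-positive rate is a poor measure of harm for a safety endpoint. This is fair: the masking in step 2 matters more than the 7% to 27% in step 4.

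Several stronger readings are tempting but not supported:
- **That the block prints nothing but adjusted contrasts.** It also prints the model summary and the Type III table.
- **That inflated p-values and an inflated false-positive rate occur together.** Step 5 shows that they cannot.
- **That confidence intervals will be missing from the report.** The calls print none by default, but the text commits to them.
- **That the ANCOVA endpoints share the defect.** HAQUAMS, HADS and EDSS have one follow-up as Table 2 reads. Their code, "tmt.means <- emmeans(mod.sec, ~ intervention") followed by `pairs()`, returns one unadjusted difference. The absent CI column is only a coding note, since the text says "Least square group differences will be reported with 95% CIs and p-values testing the null hypothesis of no intervention effect".

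**Conclusion.** The point holds for the repeated-measures endpoints, which as Table 2 reads means chiefly UNDS. Delta is not defined, and the reporting lines attach to same-visit differences an adjustment that appears nowhere in the SAP's text.

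If the code is followed, a raw p of 0.01 prints as 0.049 to 0.47 for 2 to 9 visits, and a real worsening can appear non-significant. If unadjusted p-values are used instead, the open choice allows a false-positive chance of 7% to 27%. This is an upper bound on what the choice permits, not a prediction.

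The sizes rest on an assumed visit count, because Table 2 is damaged, and the second range also on assumed between-visit correlations of 0.9 down to 0.5. The most striking figures belong to the 9-visit reading. That delta is undefined rests on neither assumption. The primary endpoint is outside this point. The change should be made, but the trial's main conclusion does not depend on it.

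**What to change.** Before unblinding, add one sentence to section 5.2 stating whether delta is the group difference at a named visit or the average over visits, given follow-up of 12 to 36 months. Then replace the reporting lines with the call that matches:

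- named visit: `summary(pairs(emmeans(var_sec, ~ intervention | time), adjust = 'none'), infer = TRUE)`, reporting the specified visit;
- average: `summary(pairs(emmeans(var_sec, ~ intervention)), infer = TRUE)`.

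Both return the difference with its 95% CI and an unadjusted p-value. Delete `contrast(tmt.means)`. If an adjustment across visits is wanted, state it in the text and restrict it to the same-visit differences.

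As a coding note, `summary(pairs(tmt.means), infer = TRUE)` in the ANCOVA block prints the CI that the text already promises.

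The cost is one sentence and a few code lines; no new data or sample-size change is needed.

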# report least square group differences
tmt.means <- emmeans(mod.sec, ~ intervention)
tmt.means
pairs(tmt.means)

```

For the Control Preference Scale, ordinal regression with logit link will be used with intervention and study centre as covariates. The model assumptions will be checked.

```

library(ordinal)
library(emmeans)

# Ordinal regression for the Control Preference Scale
mod.sec <- clm(cps ~ intervention + site, link = 'logit',
                 data = secEndpoints)
summary(mod.sec)

emmeans(mod.sec, ~ cps | intervention, mode = 'prob')

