2.7 Timing of Outcome Assessments

Data will be obtained at different time points over a period of at least 12 months and at most 36 months (on average 24 months). The trial will end when 109 relapses have been documented or after 125 PwMS have reached 24 months of follow-up. The measurement time points are calculated based on the randomization date. t_1 takes place before enrolment and t_0 before randomization, t_1 to t_{12} are scheduled every three months. Deviations from the ideal time point are allowed to the degree of ± 21 days. For all participants, who have not reached t_{12} , the final telephone interview t_x takes place after the final participant reaches t_8 . Table 2 displays the assessment of variables within these time points.

Table 2 Assessments and measurement time points**Instrument**

	Screenin	Baseline	Allocatio	Post allocation												tx
				t ₁	t ₂	t ₃	t ₄	t ₅	t ₆	t ₇	t ₈	t ₉	t ₁₀	t ₁₁	t ₁₂	
Month	t ₋₁	t ₀		3	6	9	12	15	18	21	24	27	30	33	36	X
Eligibility screen	X															
Informed consent	X															
Sociodemographic data	X	X														
Randomization			X													
Relapse history				X	X	X	X	X	X	X	X	X	X	X	X	X
Relapse questions				(X)	(X)	(X)	(X)	(X)	(X)	(X)	(X)	(X)	(X)	(X)	(X)	(X)
Decision autonomy and satisfaction				(X)	(X)	(X)	(X)	(X)	(X)	(X)	(X)	(X)	(X)	(X)	(X)	(X)
CPS relapse				X												
PAM and empowerment scale		X		X				X				X		X	X	X
HAQUMS	X							X								
HADS	X							X								
PBMS relapses			X					X								
UNDS	X							X	X	X	X	X	X	X	X	X
Relapse risk knowledge				X				X								
Physician visit including EDSS	X							X								
EQ-5D-5L	X		X				X				X		X	X	X	X
Health economic parameters	X		X	X	X	X	X	X	X	X	X	X	X	X	X	X

(x): in case of relapse

3 Statistical Principles

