5.1 Outcome definitions

A full list of outcomes and their timing is described in Section 2.7.

Ten adapted items of the **Patient Activation Measure (PAM13)** are used to assess empowerment (Zill, 2013). The items of the PAM13 range from 1 (Disagree at all) to 4 (Fully agree). The raw score is the sum of the items divided by the number of answered questions (excepting non-applicable items) and multiplied with 10. Afterwards the raw score is transformed to a range from 0 to 100 (Moljord, 2015).

$$\text{10-item PAM calculation expressed as formula: } 100 \times \frac{\left(\frac{\text{sum score}}{\text{Number of answered questions}} \times 10 \right) - 10}{(40-10)}.$$

An adapted empowerment scale with three of the five items from Bann *et al* (2010) was used to assess empowerment. The items are answered on the 3-point scale: "no," "yes, a little," or "yes, a lot."

Control Preference Scale (CPS) is used to assess preferred and realised role preference in steroid treatment decision-making. It consists of five roles ranging from A (the individual making the treatment decisions), over C (the individual making the decisions jointly with the physician) to E (the physician making the decisions). Satisfaction with the decision will be measured in a telephone interview within 3 months in case a decision for or against steroid treatment has been made.

Hamburg Quality of Life in MS Scale Version 10.0 (HAQUAMS) is a questionnaire for measuring quality of life in PwMS (Gold *et al.*, 2001). It consists of 44 items with mostly 5-point-likert scale. Twenty-eight of the items are subdivided into the six subscales:

- Fatigue: Items 6, 7, 8, 9
- Cognition: Items 10, 11, 12, 13
- Lower extremity: Items 17, 18, 19, 20
- Upper extremity: Items 21, 22, 23, 24, 25
- Communication: Items 29, 30, 31, 32, 33, 34
- Mood: Items 36, 37, 38, 39, 40.

Mean subscale scores are calculated, the total score is built by calculating the mean of the subscale score means: *HAQUAMS total score = mean(mean(upper extremity), mean(lower extremity), mean(fatigue), mean(cognition), mean(communication), mean(mood))*. Subscale and total score range from one to five; high scores indicate low quality of life. For missing items, mean substitution is allowed.

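### The CPS model makes no allowance for repeated records from one patient; if several positively correlated records enter, its confidence interval is too narrow

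*SAP*

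**What the plan says.** For the CPS, SAP section 5.2 states that "ordinal regression with logit link will be used with intervention and study centre as covariates", and the code is "mod.sec <- clm(cps ~ intervention + site, link = 'logit". The checks that follow cover proportional odds and scale effects, not independence of records.

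The response variable is left open. Section 5.1 says that the CPS "is used to assess preferred and realised role preference in steroid treatment decision-making", so there are two roles, and no section says which one is analysed. Table 1 (section 1.2) gives the endpoint only as a difference in decision autonomy measured by CPS, under an objective about autonomy in relapse treatment decisions.

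Table 2 (section 2.7) has two relevant rows. "Decision autonomy and satisfaction" carries a bracketed mark at every follow-up contact, which the footnote explains as collection when a relapse has occurred. A separate CPS relapse row carries a single unbracketed mark.

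Elsewhere in section 5.2, within-patient correlation is modelled. For the primary endpoint, "Subject-specific effects are modelled as random effects", with GEE standard errors to be explored as a fallback. The longitudinal model contains "site + (1|Patient.Id), data = secEndpoints".

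**The concern.** Randomisation is by patient (section 2.2), but a patient may have several relapses and so several treatment decisions. If each decision supplies a CPS record, records from one patient are likely to resemble each other. The specified model would treat them as independent, and with positive correlation its confidence interval would be too narrow and its p-value too small.

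The CPS is the most direct measure of the trial's hypothesis, that the programme makes relapse treatment decisions more autonomous. A difference on it will therefore be read closely, even though it is secondary.

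**Working it through.** **Plan's own figure.** The SAP gives no sample size, power or precision for the CPS. Its 81 relapses per group concern the primary endpoint. That figure reproduces (78% against 56%, two-sided 5%: 81 per group, power 85.2%) and is not in dispute.

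**Inputs from the SAP**
- 146 patients, 277 documented patient-years and 0.8775 relapses per year (section 2.3).
- Trial end at 109 relapses, or when 125 patients have 24 months of follow-up (section 2.7).
- Two-sided 5% tests and 95% intervals (section 3.1).

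**Assumptions (not in the SAP)**
- Every relapse yields one CPS record.
- Relapse counts are Poisson with mean m per patient.
- The intraclass correlation (ICC) is 0.1, 0.3 or 0.5.

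**Mean records per patient**
- If the 109-relapse criterion ends the trial: m = 109/146 = 0.75.
- If the documented follow-up of section 2.3 is reached: 277 × 0.8775 = 243 relapses, so m = 243/146 = 1.67 (1.665 before rounding).

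The expected number of patients with two or more relapses is 146 × [1 − exp(−m)(1 + m)], which is about 25 and 72.

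**Formulas.** For Poisson counts the record-weighted cluster size is 1 + m, so the design effect is DE = 1 + m × ICC. The correct interval is sqrt(DE) times as wide as the reported one, and the actual type I error is 2Φ(−1.96/sqrt(DE)).

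| m | ICC | DE | Widening needed | Type I error |
|---|---|---|---|---|
| 0.75 | 0.1 | 1.07 | 3.7% | 5.9% |
| 0.75 | 0.3 | 1.22 | 10.6% | 7.6% |
| 0.75 | 0.5 | 1.37 | 17.2% | 9.4% |
| 1.67 | 0.1 | 1.17 | 8.0% | 7.0% |
| 1.67 | 0.3 | 1.50 | 22.5% | 10.9% |
| 1.67 | 0.5 | 1.83 | 35.4% | 14.8% |

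With one record per patient, or ICC = 0, DE = 1 and there is no inflation.

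**Simulation check.** Under the null, with 15,000 trials per cell, 146 patients allocated 1:1, five categories, four assumed sites as fixed effects and a proportional-odds fit, the type I error was:

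| Setting | ICC 0 | ICC 0.1 | ICC 0.3 | ICC 0.5 |
|---|---|---|---|---|
| m = 0.75, as specified | 5.6% | 6.0% | 7.9% | 9.7% |
| m = 0.75, patient-clustered | 5.6% | 5.4% | 5.5% | 5.7% |
| m = 1.67, as specified | 5.5% | 7.0% | 10.3% | 14.1% |
| m = 1.67, patient-clustered | 5.7% | 5.7% | 5.6% | 5.6% |

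The specified model already rejects about 5.5% of the time with no correlation. At m = 0.75 and ICC 0.1, clustering therefore accounts for only about 6.0 − 5.6 = 0.4 points. With one record per patient, the specified model gave 5.6% and 5.8% and the clustered version 4.8% and 5.2%. A separate simulation without site terms (1,000 trials per cell) agrees: 8.5% and 9.7% at m = 0.75, and 11.8% and 13.5% at m = 1.67, for ICC 0.3 and 0.5.

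**The case against.** The best defence is that the SAP may intend one CPS record per patient, in which case the model is valid. Three features support this. The CPS relapse row has one mark without brackets, whereas rows collected only in a relapse use brackets. The authors add a patient term to the two models with clearly repeated records and leave it out of the baseline-plus-one-visit model, "mod.sec <- lm(var ~ intervention + var_baseline + site", so its absence here may be deliberate. Section 5.3 also speaks of analysing all patients. This stands as an open reading. It is not conclusive: the table's columns are misaligned as available, and the decision-autonomy row, the very construct that Table 1 assigns to the CPS, is collected relapse by relapse.

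A reader might go further and infer that the SAP certainly feeds repeated records into this model. The documents do not support that:
- The phrase "in case a decision for or against steroid treatment has been made" in section 5.1 describes when satisfaction with the decision is measured, not when the CPS is.
- The shared data set name secEndpoints proves nothing, since it is passed both to a repeated-measures model and to a one-record model.
- The two Table 2 rows are not an established contradiction.

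The higher error rates also need about 243 relapses. If the trial ends at 109, only the lower range applies, and any relapse without a CPS record reduces it further. The role and record may be fixed in the protocol, which is not at hand, but the SAP writes out the model and has its own section on outcome definitions.

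**Conclusion.** The point holds conditionally. The model has no protection against within-patient correlation, and the SAP does not rule out data in which that matters. Two conditions are needed for the interval to be too narrow: more than one CPS record from some patients, and positive correlation between them. It would be too strong to say that even the direction is certain without both.

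Where both hold, two-sided type I error is about 6 to 9% at 109 relapses and about 7 to 15% at about 243. These figures rest on the assumed ICC range, on Poisson counts and on one CPS record per relapse. More uneven relapse counts would raise them. Where either condition fails, there is no inflation. The change is worth making because it is at least as good as the stated method under either reading, but it concerns a secondary endpoint only. The primary relapse-level model already allows for clustering.

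**What to change.** Keep the ordinal logit model with intervention and centre. Add that patient-clustered robust standard errors will be reported whenever a patient can contribute more than one CPS record. In the same sentence, name the role analysed (preferred or realised) and the record or records used.

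An ordinal model with a patient random effect is an acceptable alternative, but one of the two should be chosen in advance. The clustered version leaves the odds ratio as specified, whereas the random effect makes it conditional on the patient.

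The cost is one or two sentences and one line of code. If records repeat, reported intervals become about 4% wider (m = 0.75, ICC 0.1) to 35% wider (m = 1.67, ICC 0.5). With one record per patient there is no material change. The change corrects only the standard error. If CPS records exist only for patients who relapse, it does not address who contributes to the comparison, which is a separate question.
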